7.1 Inclusion criteria

Japanese male or female subjects who have been confirmed to meet all the following criteria.

- (1) Hospitalized patients under treatment who were severe acute respiratory syndrome coronavirus 2 [SARS-CoV-2] positive by polymerase chain reaction (PCR) test.
- (2) Patients with clinically diagnosed pneumonia and a percutaneous oxygen saturation [SpO₂] of 93% or less on breathing of room air at bed rest.
- (3) Patients for whom written informed consent has been obtained from those themselves or the legally acceptable representatives.

(4) Patients aged 20 years or older and younger than 85 years at the time of obtaining informed consent.

[Rationale]

- Although overseas clinical studies have already preceded, Japanese patients were considered unlikely to be included in these studies. Japanese patients are to be enrolled in this study in order to evaluate the efficacy and safety in Japanese patients.
- Sargramostim was approved in the United States in 1991 and its clinical experience has been established in the market. Moreover, since no difference in safety profile between sexes has been observed in the clinical experience in patients with autoimmune pulmonary alveolar proteinosis in Japan, both sexes are to be included in the study.
 - (1) It was set in order to confirm that the patient is a COVID-19 patient.
 - (2) Considering the mechanism of action of sargramostim, the severity classification of the disease was set in reference to the current " Guide to new coronavirus infections (COVID-19) practice " ¹.
 - (3) It was set based on the Declaration of Helsinki and the GCP.
 - (4) The lower limit (20 years) was set for adults under the Japanese law.

Considering that the fatality due to COVID-19 becomes higher for patients who are elderly and also have underlying disease, patients aged 80 years and older with an underlying disease are excluded and the upper limit was set as < 85 years in order to enroll the patient population that is as close to actual clinical situation of COVID-19 as possible.

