#### 2.1.2.10.2 Secondary endpoints

##### 2.1.2.10.2.1 Changes in alveolar-arterial oxygen difference (A-aDO2) from baseline to each time point

- (1) Analysis set : FAS
- (2) Analysis item : measured values and changes in A-aDO2 (values at each time point- those at Day1)
- (3) Time point : Day 1, Day 3, Day 5, Day 10, at discontinuation/completion of treatment

(4) Analytical method :

- 1) Summary statistics (number of patients, arithmetic mean, standard deviation, median, minimum, maximum) for measured values and changes will be calculated by treatment group and by time point. In addition, a chart for the mean  $\pm$  standard deviation over time and box-and-whisker plot will be prepared by treatment group.
- 2) Estimated values of the differences between groups, 95% confidence intervals, and p-values (Day 3, Day 5, Day 10) will be calculated using mixed effect model for repeated measures (cLDA method) by time point with the measured values as the response variable, time point, treatment group, and treatment group \* time point as the fixed effects, and patients as the random effect, setting that both groups have the common mean value on Day 1. In addition, estimated values and 95% confidence intervals over time will be prepared by treatment group.
- 3) Estimated values of the differences between groups, 95% confidence intervals, and p-values (Day 5, at discontinuation/completion of treatment) will be calculated using mixed effect model for repeated measures with the measured values and changes as the response variable, baseline values as the covariate, time point (Day 1, Day 5, at discontinuation/completion of treatment), treatment group, treatment group \* time point as the fixed effects, and patients as the random effect. In addition, a chart for the estimated values and 95% confidence intervals over time will be prepared by treatment group.
- 4) The number of patients of whom changes from baseline (Day 1) decreased (improved) by 33% or more and the proportion will be calculated by treatment group and by time point (number of patients, %), and the p-values (Fisher's exact test) will be calculated.

2.1.2.10.2.2 Period from baseline to the day of discharge (days until shifting to Category 7 on a 7-point ordinal scale)

- (1) Analysis set : FAS
- (2) Analysis item : period from baseline to the day of discharge (time point - Day 0)
- (3) Time point : Day 0 to Day 28
- (4) Analytical method :

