#### 2.1.2.10.2.6 Changes from baseline in arterial blood gas values (PaO2, PaCO2, pH) to each time point.

(1) Analysis set : FAS

(2) Analysis item : measured values and changes in arterial blood gas (each time point - Day 1)

(3) Time point : Day 1, Day 3, Day 5, Day10, at discontinuation/completion of treatment

(4) Analytical method :

- 1) Summary statistics (number of patients, arithmetic mean, standard deviation, median, minimum, maximum) for measured values of arterial blood gas and changes from baseline to each time point will be calculated by treatment group and by time point. In addition, a chart for changes in the mean  $\pm$  standard deviation over time will be prepared by treatment group.
- 2) Estimated values of the differences between groups, 95% confidence intervals, and the p-values (Day 3, Day 5, Day 10) will be calculated using mixed effect model for repeated measures (cLDA method) with the measured values as the response variable, time point, treatment group, and treatment group \* time point as the fixed effects, and the patients as the random effect, setting that both groups have the common mean value on Day 1. In addition, a chart for changes in the estimated values and 95% confidence intervals over time will be prepared by treatment group.
- 3) Estimated values of the differences between groups, 95% confidence intervals, and the p-values (Day5, at discontinuation/completion) will be calculated using mixed effect model for repeated measures with the measured values of arterial blood gas and the changes from baseline to each time point as the response variables, baseline values as the covariate, time point, treatment group, and treatment group \* time point as the fixed effects. In addition, a chart for estimated values and 95% confidence intervals over time will be prepared by treatment group.
- 4) The number of patients and the proportion according to implementation status of arterial blood gas analysis (implemented, implemented while supplementing oxygen because supplementing oxygen could not be suspended, not implemented, not implemented because supplementing oxygen could not be suspended) will be summarized by treatment group (number of patients, %).
- 5) A list of outliers in  $\text{PaO}_2$  values on Smirnov-Globus test (significance level of 0.1) in any of the treatment groups will be prepared by time point.

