#### 4.7 SAS Code

- SAS Code for implementing Cox regression model is shown below.

```
ods output ParameterEstimates = [OUTPUT];
proc phreg data = [DATASET];
  class [GROUP] [THERAPY];
  model [TARGET] * [CENSOR FLG](0) = [GROUP] [THERAPY] / rl alpha = 0.05;
run;
```

- SAS Code for implementing MMRM model is shown below.

```
proc mixed data = [DATASET];
  class [SUBJECT] [VISIT] [GROUP];
  model CHG = BASE [VISIT] [GROUP] [VISIT] * [GROUP] /ddfm = KR;
  lsmeans [GROUP]* [VISIT];
  repeated [VISIT]/ subject = [SUBJECT] type = UN;
```

run;

- SAS Code for implementing analysis using generalized estimating equation is shown below.

```
proc genmod data = [DATASET];
  class [SUBJECT] [VOLUME] [GROUP];
  model CHG = [GROUP] [VOLUME] [GROUP]* [VOLUME] ;
  lsmeans [GROUP]* [VOLUME];
  repeated subject = [SUBJECT] type = UN or CS;
run;
```

- SAS Code for implementing analysis using MMRM model (cLDA method) is shown below.

\* The coefficient of Estimate must be changed to suit the data.

\*The value of DIF3, DIF5, and DIF10 in the active group is 1 at each time point, otherwise 0.

```
proc mixed data = [DATASET] order = internal;
  class AVISITN(ref = "1") USUBJID;
  model AVAL_ = AVISITN DIF3 DIF5 DIF10/noint s ddfm = kr;
  random USUBJID;
  /* difference between groups in each time point*/
  estimate "Diff (NPC-26 - Placebo) Day3" DIF3 1 /cl;
  estimate "Diff (NPC-26 - Placebo) Day5" DIF5 1 /cl;
  estimate "Diff (NPC-26 - Placebo) Day10" DIF10 1 /cl;
  /* Mean CHG in each time point in each group */
  estimate "LSMean of Change from BL (Placebo) Day3" AVISITN 1 0 0 -1 /cl;
  estimate "LSMean of Change from BL (Placebo) Day5" AVISITN 0 1 0 -1 /cl;
  estimate "LSMean of Change from BL (Placebo) Day10" AVISITN 0 0 1 -1 /cl;
  estimate "LSMean of Change from BL (NPC-26) Day3" AVISITN 1 0 0 -1 DIF3 1 /cl;
  estimate "LSMean of Change from BL (NPC-26) Day5" AVISITN 0 1 0 -1 DIF5 1 /cl;
  estimate "LSMean of Change from BL (NPC-26) Day10" AVISITN 0 0 1 -1 DIF10 1 /cl;
  /*Mean AVAL in each time point in each group */
  estimate "LSMean (Placebo) Day1" AVISITN 0 0 0 1 /cl;
  estimate "LSMean (Placebo) Day3" AVISITN 1 0 0 0 /cl;
  estimate "LSMean (Placebo) Day5" AVISITN 0 1 0 0 /cl;
  estimate "LSMean (Placebo) Day10" AVISITN 0 0 1 0 /cl;
  estimate "LSMean (NPC-26) Day1" AVISITN 0 0 0 1 /cl; *This is same as in common with
Placebo;
  estimate "LSMean (NPC-26) Day3" AVISITN 1 0 0 0 DIF3 1 /cl;
  estimate "LSMean (NPC-26) Day5" AVISITN 0 1 0 0 DIF5 1 /cl;

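### The blood-gas cLDA assumes equal variance at every visit, so its Day 5 standard error is wrong if spread changes, and too small if oxygenation spreads out after baseline

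*SAP*

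**What the plan says.** SAP 2.1.2.10.2.1 item 2 (A-aDO2) and SAP 2.1.2.10.2.6 item 2 (PaO2, PaCO2, pH) plan a constrained longitudinal model for the group differences on Days 3, 5 and 10. The A-aDO2 text specifies "patients as the random effect, setting that both groups have the common mean value on Day 1"; the blood-gas section specifies the same structure.

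The code in SAP 4.7 agrees. Its mean model is "model AVAL_ = AVISITN DIF3 DIF5 DIF10/noint s ddfm = kr", and its only covariance statement is "random USUBJID". There is no repeated statement and no empirical option.

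The other repeated-measures code in SAP 4.7 has "repeated [VISIT]/ subject = [SUBJECT] type = UN", which lets each visit have its own variance. That is the model for item 3 of the same two sections, which also yields a Day 5 difference, interval and p-value.

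Entry requires a screening SpO2 "of 93% or less on breathing of room air at bed rest" (Protocol 7.1). The blood-gas baseline is the pre-dose sample on Day 1 (Protocol 5.2.1.2 and 5.2.1.6).

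**The concern.** A random patient intercept with independent residuals implies compound symmetry: one variance at all visits and one correlation between all pairs of visits. The Day 5 standard error is then built from a variance averaged over visits. If Day 5 is more variable than that average, the interval is too narrow and the test rejects too often.

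For oxygenation this is plausible. The entry criterion cuts off the better-oxygenated side shortly before Day 1, and no such limit applies on Day 5, when some patients will have recovered and others not. Kenward-Roger adjusts the degrees of freedom and makes a small-sample correction. It does not repair a wrong covariance structure.

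What is at stake is the Day 5 comparison. A-aDO2 is the first-listed secondary endpoint, and Protocol 6.3 partly rests the dose rationale on an interim A-aDO2 result of p=0.053 from another study. A result near 0.05 is therefore realistic here, and a standard error wrong by 10–15% could change how it is read.

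**Working it through.** **Inputs from the documents.** 40 active and 20 control patients (Protocol 18); two-sided 5% (SAP 2.1.2.12); random intercept only (SAP 4.7). Blood gas is scheduled on Day 1, Day 5 and at a discontinuation/exit test (Protocol 2). Day 3 and Day 10 values arise when that exit test falls on those days (SAP 2.1.2.14 item 5).

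**Inputs assumed.** The documents give no blood-gas SD or correlation. Write r for SD(Day 5)/SD(Day 1), with Day 1 SD = 1 and r = 1 to 2. Let ρ be the Day 1–Day 5 correlation, 0.3 to 0.7.

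**The plan's own figure.** The only stated operating characteristic is 82.1% log-rank power for the primary endpoint. It reproduces (82.2% with continuous times, 4000 runs). It supports the 40:20 sizes but says nothing about blood gas.

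**Step 1: Day 1 and Day 5 only.** The equal-variance fit settles on the pooled variance v = (1+r²)/2 and keeps the covariance ρr, so its fitted correlation is c = ρr/v. With a common Day 1 mean, the estimated effect is the Day 5 group difference minus c times the Day 1 group difference. Let k = 1/20 + 1/40 = 0.075.

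- Variance the model reports: v(1−c²)k.
- True variance: (r² − 2cρr + c²)k. Because ρr = cv = c(1+r²)/2, this equals r²(1−c²)k.
- Model SE / true SE = √(v/r²) = √((1+r²)/(2r²)). The correlation cancels.
- Large-sample type I error = 2Φ(−1.96 × ratio).

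At r = 1.5: v = 3.25/2 = 1.625; ratio = √(1.625/2.25) = 0.850; 1.96 × 0.850 = 1.67, giving 9.6%. With ρ = 0.5 the model reports 0.310 against a true 0.364. An unstructured fit has SE 1.5 × √0.75 × √0.075 = 0.356.

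**Step 2: other visit patterns.** Here the compound-symmetry parameters that best fit the assumed covariance were found numerically, with ρ = 0.5 and SD stepping up once after baseline. The protocol-schedule column assumes 5% of patients stop on Day 3 and 20% reach Day 10. Each cell gives the SE ratio and type I error.

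| r | Days 1 and 5 only | Protocol schedule | All four visits complete |
|---|---|---|---|
| 1.00 | 1.000; 5.0% | – | – |
| 1.25 | 0.906; 7.6% | 0.914; 7.3% | 0.951; 6.2% |
| 1.50 | 0.850; 9.6% | 0.863; 9.1% | 0.919; 7.2% |
| 2.00 | 0.791; 12.1% | 0.807; 11.4% | 0.882; 8.4% |

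On the protocol schedule the SE is 8.6%, 13.7% and 19.3% too small.

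**Step 3: check by simulated REML fits, 60 patients.** On the same assumed schedule, one set of runs gave Day 5 type I error of 8.3% at r = 1.5 and 11.5% at r = 2.0. A separate set of 700 gave 10.6% at r = 1.5 (Monte Carlo margin 1.96 × √(0.106 × 0.894/700), about 2.3 points). Two visits with ρ = 0.7 and r = 1.5 gave 9.4% (1500 runs). With equal variances the rate was 5.3% (2000 runs).

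**Step 4: where the direction changes.** The exact condition is that Day 5 variance exceeds the visit-pooled variance.

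- SDs of 1, 1.1, 1.25 and 2 on Days 1, 3, 5 and 10, with 50% or all patients measured on Day 10: ratio 1.10 or 1.14, so the SE is too large.
- Steady widening (1, 1.25, 1.5, 2) over four complete visits: ratio 0.99.
- Narrowing (r = 0.8, two visits): ratio 1.13.

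**Step 5: how much could truncation alone do?** Assume 30–70% of patients pass the cut, screening-to-Day 1 correlation is 0.6–1.0 and Day 1-to-Day 5 correlation is 0.3–0.7. Then r runs from 1.06 to 1.87, the SE ratio from 0.97 to 0.80 and type I error from 5.6% to 11.6%.

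**Step 6: candidate remedies on the assumed schedule.** Compound symmetry with a sandwich variance gave about 5.5% on Day 5 but about 14% on Day 10, against 4–8% on Day 10 for the planned model (500 runs). A heterogeneous-variance structure gave 4–6% on both days and lost nothing when variances were equal.

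**The case against.** A reader might infer that the trial's Day 5 A-aDO2, PaO2 and PaCO2 results will all have intervals that are too narrow and a type I error above 5%. The documents do not support that, for these reasons.

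- **A second Day 5 analysis exists.** Item 3 of both sections compares the groups on Day 5 with a model coded as unstructured, which does not assume equal variances. This stands. It is not a perfect safeguard: the A-aDO2 text of item 3 also names patients as a random effect and lists Day 1 as a time point, neither of which fits that code, and the SAP does not say which Day 5 result takes priority.
- **The widening is assumed.** No SD is given for any visit. This stands, and the conclusion is conditional for that reason.
- **The truncation argument is loose.** The cut is on screening SpO2, which may date from up to 7 days before consent (Protocol 13), not on the Day 1 gas. It is one-sided, so the severe tail stays open at baseline. The safety check before room-air sampling (Protocol 13.10) may remove the sickest patients on Day 5, which limits widening. All of this stands. The criterion also gives no mechanism for PaCO2 or pH, so the argument for direction covers A-aDO2 and PaO2 only.
- **The direction can reverse.** Step 4 shows this. But with few Day 3 values on the documented schedule, Days 1 and 5 should dominate the pooled variance unless many patients reach Day 10 and spread grows mainly by then. An SE that is too large is also wrong and has the same remedy.
- **A four-visit unstructured matrix would not work.** On the scheduled visits no patient has both a Day 3 and a Day 10 value, so that covariance cannot be estimated. This stands, and it means that using unstructured in one model and not the other is not a simple inconsistency. It does not justify equal variances, because intermediate structures exist.
- **These are secondary endpoints without multiplicity control** (SAP 2.1.2.13). This limits the consequence but does not make the standard error right.

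**Conclusion.** The point holds in conditional form. The cLDA code imposes equal variances that nothing in the documents supports, and no check is planned. If oxygenation widens after baseline on the protocol schedule, the Day 5 SE from this analysis is about 9%, 14% and 20% too small at SD ratios of 1.25, 1.5 and 2.0, with type I error of about 7%, 8–10% and 11–12%.

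Those ratios are assumptions, as are the share of patients with Day 3 and Day 10 values and the correlation of 0.5. With no change in spread there is no loss. With loose truncation and no other source of widening, the SE may be only about 3% too small. With late widening and many Day 10 values, it is too large.

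The effect is confined to item 2 of the two blood-gas sections. The item 3 model as coded and the primary log-rank analysis are not affected. The point is worth correcting because the correction is cheap; it does not threaten the trial's main conclusion.

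**What to change.** In the cLDA code, replace the random statement with a heterogeneous-variance repeated structure, for example `repeated AVISITN / subject=USUBJID type=CSH`, and keep Kenward-Roger. Amend item 2 of SAP 2.1.2.10.2.1 and 2.1.2.10.2.6 to match.

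Pre-specify what happens if Day 3 or Day 10 data are too sparse for a separate variance at each visit. Either use one baseline variance and one common post-baseline variance, or fit Days 1 and 5 alone with `type=UN` for the Day 5 contrast.

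Two alternatives should be avoided: a four-visit unstructured matrix, which the scheduled visits cannot identify, and compound symmetry with a sandwich variance for the sparse Day 10 contrast.

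The cost is one line of code, a short SAP edit and one to three more covariance parameters. The planned model has 2. CSH over four visits has 4 variances and 1 correlation, so 5. Either fallback has 3.
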